We propose to enrol 200 young women (18-35 years) at two Sites (100 at the Desmond Tutu Health Foundation, Masiphumelele CRS, 100 at the Kenya Medical Research Institute, Lumumba clinic, and Kargeno Research and Policy Hub, Kisumu CRS). Eligibility criteria will include being HIV-uninfected with no other serious comorbid illnesses, having no clinical or microbiological evidence of BV/STIs at screening, not being pregnant, not having taken antibiotics in the past month, and having no history of cervical disease. All CRSs have extensive experience enrolling women into HIV-related and reproductive health research in Africa. After enrolment, written informed consent will be obtained from participants before performing any procedures. In addition, we will seek consent that vaginal lactobacilli strains isolated through this study can potentially be included in a formulation to treat BV for women in Africa. We will also seek consent for the isolation of additional species (e.g. *Prevotella bivia*, *Gardnerella vaginalis*, etc) for research purposes. At enrolment, a detailed interviewer-assisted questionnaire will be administered assessing demographics, behaviour (sexual and vaginal practices), menstrual and health history, contraceptive choice, based on our previous Questionnaires.

Fig 2. Inclusion/Exclusion

Inclusion Criteria	Exclusion Criteria
Female at birth	Male at birth
Willing and able to provide informed consent and cognitive ability to understand sampling procedures	Not willing to provide informed consent
Not pregnant	Pregnant or planning to become pregnant in the next 10 weeks
HIV-	HIV+
18-35 years old	<18 or >35 years old

Sexually active for the last 3 months defined as penetrative penile-vaginal intercourse at least once in the last 3 months	No penetrative penile-vaginal intercourse in the last 3 months
Planning to stay in the area for the next 10 weeks	Planning on moving, going away out of area within the next 10 weeks
Willing and able to return for all 3 nurse visits and return self-swabs to the clinic weekly	On chronic disease management for gynaecological conditions
Able and willing to provide adequate locator information for study retention purposes	Unable to return for all 3 nurse visits and return self-collected swabs to the clinic weekly / Unable to agree to adhere to all study visits and procedures
	Bacterial vaginosis
	Untreated STI
	Currently taking an antibiotic or antibiotic use in the last four weeks

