	Any medical condition or other factors which would preclude study participation as per principal Investigator's or designee's decision, including but not limited to cancer of the cervix
	Any mental health condition which, in the opinion of the investigator, would preclude comprehension of informed consent, or preclude study participation.

Sample Size

Prior studies by our groups have demonstrated the vaginal microbiota of reproductive-aged women can be clustered into 5 major CSTs (*Lennard et al. 2018; Balle et al. 2020*). In order to ensure that our study yields interpretable results, enough women need to be sampled so that each of the 5 CSTs are represented. To determine the number of women that must be sampled, we propose to follow an approach adapted from Abdo et al. (*Abdo et al. 2006*). Assuming that the proportions reported in our previous studies (including the uCHOOSE cohort (*Balle et al. 2020*) and the WISH Cohort (*Lennard et al. 2018*), correspond very closely to the population frequencies of CSTs and that they are preserved over time, Abdo et al. derived an equation $\sum_{i=1}^5 p_i^n = \alpha$ which when solved for n, determines that the study needs at least 100 women in order to obtain data on all five CSTs with 80% probability, where $\alpha=0.05$ and p_i is the probability of missing the i-th CST estimated as $1 - (\text{frequency of the i-th CST})$. In particular, we estimate that ~20% of young women enrolled through both CRSs would have

CST I vaginal microbiota that appears to be relatively stable over time. Thus, with a cohort of 200 women, we therefore expect ~40/200 of the participants will cluster into CST I.

Questionnaires and daily diaries to record exposure to sex and antibiotics

A detailed interviewer-assisted questionnaire will be administered assessing demographics, behaviour, sexual and vaginal practices, menstrual and health history, contraceptive choice, based on questionnaires from our previous studies in the same populations (*Barnabas et al. 2018*). In addition, daily diaries will model those previously used by Gajer et al. (*Gajer et al. 2012*) in the form of a yes/no check-off list to report menstrual bleeding; vaginal douching; sexual activity; use of medications or contraceptives, diaphragm, and sanitary care (including sanitary pads, cloths, newspaper, menstrual cups and/or tampons). Like the swabs, behavioural diaries will be submitted to the study site weekly. Data will be captured using RedCap.

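### Sample Size: alpha of 0.05 in the stated equation gives at least 95% probability of observing all five CSTs, so it cannot go with the 80% in the same sentence

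*Protocol*

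**What the plan says.** The Sample Size section of the protocol starts from earlier cohorts in which the vaginal microbiota "can be clustered into 5 major CSTs", and makes representation of each type the condition for interpretable results. Its method is adapted from a cited paper, whose authors are said to have "derived an equation $\sum_{i=1}^5 p_i^n = \alpha$ which when solved for n" gives the required number of women. The terms are defined in the same sentence: "where $\alpha=0.05$ and p_i is the probability of missing the i-th CST", estimated as one minus that type's frequency. The conclusion is that the study "needs at least 100 women in order to obtain data on all five CSTs with 80% probability, where" alpha is 0.05.

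The frequencies are taken from two earlier cohorts ("Assuming that the proportions reported in our previous studies" hold in the population and over time) but are not listed. The one planning value printed is for CST I: "we estimate that ~20% of young women enrolled through both CRSs would have" it, which the section turns into about 40 of 200 participants.

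On enrolment, the section on study population and eligibility says "We propose to enrol 200 young women (18-35 years) at two Sites", 100 in each country. The later sample-size heading under Statistical considerations only refers back to the Sample Size section.

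**The concern.** In this equation alpha is the tolerated probability of failing to see every CST. It is not a significance level that sits beside a separate power. The probability of success is therefore tied to alpha, and 0.05 and 80% cannot both belong to it. One of the printed figures is wrong, or the equation is misdescribed.

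The only design probability that the protocol states cannot be relied on as written. A reader cannot tell whether 100 women have roughly a 5% or a 20% chance of leaving a CST unobserved. The objectives concern different geographies and each country contributes 100 women, so this bears on whether one country's cohort will contain all five types.

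**Working it through.** **Inputs from the protocol.** Five CSTs; p_i = 1 − f_i, where f_i is the frequency of type i; equation Σ p_i^n = alpha; alpha = 0.05; n = 100; stated probability 80%; CST I about 20%; enrolment 200, 100 per country. The other four frequencies are not given.

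**Step 1: what the equation fixes.** p_i^n is the probability that none of n women has type i. By the union bound, P(at least one type missed) ≤ Σ p_i^n = alpha, so P(all five seen) ≥ 1 − alpha.
- alpha = 0.05 gives at least 0.95.
- alpha = 0.20 gives at least 0.80.

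**Step 2: can slack in the bound explain the gap?** No. The bound overstates the probability of a miss by at most the sum of the pairwise products of the five terms p_i^n. For five terms adding to alpha, that sum is at most 10 × (alpha/5)² = 0.4 × alpha².
- alpha = 0.05: 0.4 × 0.0025 = 0.001, so P(all five) lies between 95.0% and 95.1%.
- alpha = 0.20: 0.4 × 0.04 = 0.016, so P(all five) lies between 80.0% and 81.6%.

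The gap to explain is 15 percentage points. Exact inclusion-exclusion calculations at n = 100 agree: 95.0% to 95.1% where Σ p_i^100 = 0.05, and 80.0% to 81.2% where it is 0.20. The plan's 80% is not reproduced from alpha = 0.05 under any frequencies.

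**Step 3: can n = 100 be checked?** Not from this document. If one rare type dominates the sum, (1 − f)^100 = alpha gives f = 1 − 0.05^(1/100) = 2.95% for alpha 0.05, and f = 1 − 0.20^(1/100) = 1.60% for alpha 0.20. Either is possible.

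**Step 4: how far apart are the two readings?** Assume CST I at 20%, m equally rare types and the remainder common. The ratio of the n for 95% to the n for 80% is then close to ln(0.05/m) / ln(0.20/m).

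| m | ratio | if 100 is the 80% figure, n for 95% | if 100 is the 95% figure, n for 80% |
|---|---|---|---|
| 1 | 1.86 | 187 | 54 |
| 2 | 1.60 | 161 | 63 |
| 3 | 1.51 | 152 | 67 |

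Three further frequency sets, all assumed (CST I first, in %), with n rounded up:

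| frequencies | n for 95% | n for 80% | ratio | P(all five), n = 100 | n = 200 |
|---|---|---|---|---|---|
| 20/3/32/40/5 | 103 | 61 | 1.67 | 94.7% | 99.8% |
| 20/2/33/40/5 | 149 | 84 | 1.79 | 86.2% | 98.2% |
| 25/2/33/38/2 | 183 | 114 | 1.60 | 75.2% | 96.5% |

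**Step 5: the pooled cohort.** If Σ p_i^100 = 0.20, then Σ p_i^200 ≤ 0.20² = 0.04, so 200 women see all five with at least 96% probability. If Σ p_i^100 = 0.05, then Σ p_i^200 ≤ 0.05² = 0.0025, so at least 99.75%. This uses the same frequencies in both countries.

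**Step 6: the other planning figure.** 20% of 200 = 40, which agrees with the protocol.

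**The case against.** Four points can be made for the protocol.

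- **Low stakes for a pilot.** This is an observational cohort with no hypothesis test or decision rule that uses alpha. Its primary outcomes are a collaboration agreement, public data and a biorepository. This stands, and it keeps the severity at moderate.
- **The cohort is twice the stated minimum.** The text says that the study needs 100 women, and 200 are enrolled. This also stands: Step 5 puts the pooled cohort at 96% or more on either reading. What remains is representation within one country.
- **The 0.05 may apply to each type separately.** Four types each missed with probability 0.05 give 0.95^4 = 81%, which is close to 80%. But the printed equation sums over all five types and sets the total to alpha. Applied separately to five types, 0.05 gives 0.95^5 = 77%.
- **The method is adapted from a paper not at hand, and the frequencies are in cited cohorts.** This does not reconcile the printed sentence. It does leave open which element is the slip, and it means only that n = 100 cannot be reproduced from the protocol alone.

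A reader might also infer that the formula is offered as the justification for 100 women per site. The section does not say so. It gives 100 as the study's minimum and does not say whether the figure is meant per country or overall.

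**Conclusion.** The Sample Size statement is internally inconsistent. With alpha of 0.05 the equation gives a probability of at least 95% (at most 95.1%) of observing all five CSTs, not 80%. This needs no assumption about the frequencies.

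The size of the consequence does rest on assumed frequencies. The n for 95% is about 1.5 to 1.86 times the n for 80%. The upper end is the limiting case of a single rare type.

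Two stronger readings are tempting and unsupported. One is that 100 women in fact deliver 95%. The other is that enrolment is too small. With four of the five frequencies missing, n = 100 can be neither confirmed nor refuted. If 100 is correct for either probability, the pooled 200 are ample for this criterion. If 100 is the 80% figure, each country's 100 women have about a one-in-five chance of lacking at least one CST, assuming that country has the planning frequencies. Severity is moderate.

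**What to change.** Restate the paragraph in the Sample Size section:

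- Give one matched pair, either at least 95% with alpha of 0.05 or at least 80% with alpha of 0.20, whichever the sponsor's own frequencies support at n = 100. If they support neither, correct n as well.
- List the five CST frequencies used and the cohort each comes from.
- Say whether 100 is a per-country or an overall requirement, and give the resulting probability for 100 women per country and for 200 overall.

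The later sample-size heading, which refers back, then needs no change. The cost is one rewritten paragraph and a short recalculation from frequencies the sponsor already has, with no change to planned enrolment or procedures.

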[name] (<https://www.linkedin.com/in/[name]>) is a Clinician researcher at DTHF and Clinical Research Site Director at Masiphumelele, Cape Town where the South Africa part of the study will be done. [name] has more than 10 years of experience working in HIV/TB clinical management, grant management, and clinical research, running the Masiphumelele research site which specializes in HIV Prevention Clinical Trials and COVID research. [name] has been collaborating closely with [name] for more than 5 years on the uCHOOSE study, which focused on hormone contraceptive choices in adolescents in a randomized cross-over trial.

Data Collection and Handling

The investigator agrees to maintain accurate source documentation and case report forms. For each participant screened, an electronic CRF (eCRF) will be completed, even if the participant drops out at any time during the study. All eCRF information for the completed visits must be completed.

All applicable eCRF pages must be completed for each subject who has completed the study. For participants who are prematurely withdrawn, the visits up to withdrawal plus the withdrawal visit need to be completed. In the case of necessary corrections, all changes will be effectuated such that the first version is still legible, and the change is initialled and dated by the correcting person.

Data entered into the eCRF is, on saving the eCRF, stored in a web-based database, hosted on a secure server at UCT (RedCap). The database will have user access control, and all changes are tracked in an audit trail. Further, data quality is ensured by a series of pre-programmed edit checks to ensure plausibility, and by manual curation by a professional data manager. The server is subject to regular backups and access control.

Source Documents

Source data is defined as all information in original records and certified copies of original records of clinical findings, observations, or other activities in a clinical trial necessary for the reconstruction and evaluation of the trial. Source documents will include, but are not limited to, progress notes, electronic data, screening logs, and recorded data from automated instruments. Study data will be directly entered into the electronic CRF, in which case the eCRF is the source. Some data may still be captured entirely or partially on paper source documents, and may then manually be entered into an eCRF, including but not limited to:

- Informed Consents
- Sample collection data (may be on Lab Forms), and

- Laboratory results and their review by the investigator
- Participant locator information

All paper source documents and the electronic source documents pertaining to this trial will be maintained by the investigators. The investigator has to permit trial-related monitoring, audits, Independent Ethics Committee/Institutional Review Board (IEC/IRB) review, providing authorized persons direct access to source data/documents.

Study Assessments

Demographic and Background Assessment

- Written informed consent
- Eligibility assessment
- Demographic data: date of birth, gender
- Targeted physical exam including Weight in kilograms (kg) and Height in meters (m)
- Social history (sexual risk behaviour)
- Information about the recent or current antibiotic use
- “Key informant” socio-economic questionnaire on the household
- Locator information including address and contact information (names and phone numbers)
- Clinically significant medical and treatment history (including HIV status, ART, IPT and previous TB episodes, diabetes)
- Questionnaire on socio-economic, exposure and risk parameters
- STI symptom screen

Pre-test counselling

The counselling process will be conducted to address individual HIV risk in the language that the participant understands. The information session will include the following key components if appropriate to the circumstances:

- Information about HIV acquisition and transmission.
- Emphasis on the importance and advantages of early HIV testing to facilitate diagnosis, positive living, and healthy lifestyle.
- Information about the HIV testing process.
- Discussion on confidentiality and shared confidentiality.
- Discussion on the option not to take the test.
- Offer an opportunity to test at a later date should the client decline the test.
- The importance of TB symptomatic screening during pre- and post-test counselling.
- Referral to HIV and AIDS related services
- Importance of partner testing, especially in ANC settings.

- Information about effective HIV prevention measures, including consistent and correct use of condoms, partner reduction, and other options.

In addition, if time permits the provider may also discuss the following components as appropriate to the circumstances:

- Assessment of individual risk and when a possible exposure may have occurred.
- Determining whether there is a history of domestic violence.
- Discussion on partner involvement and referral for testing.

Pregnancy urine test

A urine pregnancy test will be used to identify raised HCG. The test will be performed in the lab and read at 3 minutes or as test manufacturer recommendations.

HIV rapid

A single-use rapid immunoassay for the qualitative detection of antibodies to HIV-1 and HIV2 intended for use in point of care settings as an aid in diagnosis of HIV-1 and HIV-2 infection will be used and read at 20 minutes or as test manufacturer recommendations.

*HIV + confirmatory test

A confirmatory test in cases where the screening test is reactive will be ordered. The preliminary result will be verified with a second rapid test that works in a slightly different way.

Post-test counselling

All participants, regardless of the outcome of the HIV test, will be offered and receive post-test counselling based on their test result. All results will be given clearly in a language the participant is most comfortable with. The length of the post-test counselling session will vary based on the test result. The post-test counselling prevention package will include information and advantages of TB screening, risk reduction and correct and regular use of condoms. Depending on the participant's circumstances there may be a need for them to retest for HIV. The participant may be encouraged to bring their partner in for couples testing, depending on the client's circumstances. there may be a need for them to re-test for HIV. See section 4.5 for when to recommend re-testing. The participant may further be referred for additional prevention counselling if the participant reports ongoing risk.

Physical Examination

The physical examination may include:

- height and weight measurements
- nose, mouth, throat, and ear examination with a torch or scope

- Vitals
- checking the body's reflexes
- listening to the heart and lungs with a stethoscope
- feeling the lymph nodes in the neck, underarms, or groin
- feeling the abdomen to check for abnormalities

Amsel Test

- 1x lateral wall vaginal wall swab to be applied to a pH indicator, used for wet mount preparation and applied to a second glass slide for the whiff test (addition of a few drops of 10% potassium hydroxide solution).
- Description of any vaginal discharge

Speculum Exam

Will include:

- physical examination of the vagina, vulva
- Insertion of a speculum for examination of the cervix
- checking for any abnormalities that may be indicative of cancer, sexually transmitted disease, or other benign conditions
- Swabs for STI and BV testing

STI testing

1x Vulvo-vaginal swab and 1x high vaginal wall swab will be taken for STI and BV testing

Testing will include:

- Chlamydia (SA + Kenya)
- Gonorrhoea (SA + Kenya)
- Trichomoniasis (SA + Kenya)
- Herpes Type 1 & 2 (Kenya)
- Mycoplasma genitalium (Kenya)

Nugent scoring

1x lateral vaginal wall swab to be applied to the pH indicator and rolled on a glass slide. Nugent score on Gram smears will be used as the diagnostic test that defines normal vaginal flora, BV, or intermediate abnormal flora.

ITS and 16S rRNA microbiome sequencing

1x lateral vaginal wall swab for qPCR and 16S rRNA (bacterial) & sequencing (Molecular transport medium [Qiagen]). ITS of nuclear DNA will be used as a target for analysing fungal diversity in the genital samples, as the standard marker for fungal DNA barcoding.

Cytokine Measurement and HPV genotyping

1x soft cup will be used for the cytokine measurements (supernatant) and HPV genotyping (pellet).

Long-term sample storage (Bio-bank)

1 X lateral vaginal wall swab for culture and storage (Amies-based transport solution, eg Eswab for culture)

2 X lateral vaginal wall swabs stored for use in future studies (proteomic and metabolomic, swabs stored in protective buffer and dry respectively)

1 X cytobrush stored for use in future studies (transcriptomic)

Samples from VMRC4Africa Pilot participants will be stored for three purposes:

Perform experimental assays and sub-studies, after end of recruitment and follow-up of participants

Long-term storage for further research on yet undefined diagnostics and other infectious disease research questions

Product formulation

Both short- and long-term storage samples will be cryopreserved at the recruiting health research institutions or designated laboratories in their countries. Long-term storage of samples will only be permitted for samples of participants who have signed the sample storage and future use consent.

Participant enrolment

A total of 200 women will be enrolled at two sites (Cape Town, South Africa, and Kisumu Kenya). Participants who meet all of the inclusion criteria and none of the exclusion criteria will be followed intensively for 10 weeks. Eligible participants will be enrolled in line with their menstrual cycle to avoid blood contaminated genital samples for processing and storage. Those who are deemed eligible but present with recent antibiotic use or treatable STIs will wait 28 days post antibiotic treatment before enrolment. Thus, screening to exit may be extended to 16 weeks if appropriate.

Recruitment process

Participants will be recruited via the CRS standard recruiting process. Participants will be informed about the study via social media, flyers and posters.

Each site will use a variety of recruitment approaches that works best for the local setting. Recruitment may be conducted through the following possible approaches: community events and mobilisation, partnerships with appropriate programs and via popular social media platforms. Recruitment materials will educate women about HIV, sexual health, and risks in their community, the effectiveness of PrEP for HIV prevention, and the benefits of HIV prevention services. Recruitment will occur over approximately 12 months.

Recruitment strategy DTHF.

The Masiphumelele Research Office is strategically positioned on the outskirts of a discreet, relatively moderate sized township community (Masiphumelele) and in close proximity to a second low socioeconomic, high-density community (Ocean View). It has easy access to a population of >50 000 people. In close proximity, there are also a number of middle-class suburbs with a combined population of >50 000 people. The site is planning to recruit in all of these areas via the two primary care clinics in Masiphumelele and Ocean View and the district hospital in Fish Hoek.

The site actively tracks research visits and sends reminders to participants before each visit window opens. The site also pro-actively follows up with participants who have missed target dates to avoid missed visits. The site will also do home visits and transport participants to and from the site as needed.

Recruitment strategy KEMRI.

Recruitment will take place in Kisumu city and its environs. We will work with staff at strategic pharmacies and maternal child health/family planning (MCH/FP) clinics to identify potential participants and refer them to the study staff for recruitment based on our eligibility criteria. At the community level, study staff members will work with community health volunteers (CHVs) where possible, to sensitize potential participants about the study and directly refer potential participants to the study staff or give phone contacts to those interested to participate in the study to call the study team for additional information about the study. Study staff will also carry out door-to-door recruitment of women within the community to complement the recruitment done by CHVs. Study staff will leverage community meetings/gatherings to sensitize the community on the study and identify potential participants for recruitment. Recruitment activities will be conducted in line with current COVID-19 infection prevention measures and guidelines to ensure safety of both participants and staff.

All materials to advertise the study (leaflets and posters) will be used only upon approval of the ethics committees and/or regulatory authorities relevant for this study. The investigator or delegate may discuss certain aspects of the study with potential participants before consenting, e.g. to determine eligibility/ pre-screening.

Participant informed consent

Participants who fit the eligibility criteria will be invited to join the study. They will be given an informed consent form (ICF) about the study and will be explained the anticipated benefits and the potential risks associated with the protocol procedures. The principal investigator (PI) or designee will fully inform the participant, or the participant's legally acceptable representative. The language used will be as non-technical as possible and the participant will not unduly be influenced to participate in the study. Participants will be informed that they may voluntarily withdraw from the study for any reason at any time, and a withdrawal will have no negative effects on them receiving standard care afterwards.

Written consent must be obtained from every participant prior to any procedures being done specifically for the study.

An impartial witness is required for the entire informed consent process for any participant who is illiterate or whose literacy is limited. Documentation of the presence of a witness will be achieved through their signature on the informed consent document. Illiterate participants will indicate their consent via use of their mark (finger/thumb print) on the informed consent documents.

The signed original ICF will be kept with the Investigator Site File at the site. A second original of the signed informed consent form, will be given to the participant or to the participants' legally acceptable representative. The site will document the name and position of those persons at the site who are responsible for obtaining informed consent and no other staff will perform this.

In the event any modifications to the ICF are proposed, the consent form will be re-submitted to the ethics committee for approval. The ICF will be revised whenever new important information becomes available. All active participants will additionally sign all revised ICFS, after ethics approval is received.

Incentives and expenses

Participants will not receive any incentives for their participation in the study. However, participants will be reimbursed for their time and transport costs to the research clinics. The exact amount will be decided by each of the sites and informed by the community advisory committees.

Participant withdrawal and/or loss to follow-up

A participant may decide to withdraw from the study at any time and for any reason. The investigator may also withdraw a participant for any of the following reasons:

- Participant is unwilling or unable to comply with required study procedures
- If, for any reason, the investigator concludes that continued participation in the study would not be in the participant's best interest
- Early study termination

When a participant withdraws or becomes lost to follow-up from the study, the reason(s) for withdrawal or lost to follow-up shall be recorded by the investigator or designee in participants' study records.

Should a participant become HIV positive or pregnant after enrolment, they will be allowed to continue to attend clinic visits and participate in the interviews/questionnaires if they choose to do so. This is to reduce the potential impact of stigma associated with a positive HIV diagnosis and/or unplanned pregnancy. However, no further mucosal samples will be collected, since for HIV positive participants this poses an additional risk to study personnel who will need to handle and process potentially infectious samples and for pregnant participants, the additional discomfort and risk associated with speculum exam and sampling are difficult to justify given that they will not be included in the study analysis.

Participants who become infected with an STI after enrolment (TV, NG, CT) will be referred for treatment, but can continue to provide samples should they choose to do so.

Study procedure

Screening

Potential participants identified will be invited to be screened for inclusion in the study. Before any study-specific screening procedures will be performed, all participants will sign and date (or thumbprint) the latest version of the ICF. Illiterate participants will be encouraged to have an independent witness present. Once a participant has signed a consent form, their details, including date and participant number, will be registered on a screening log.

After informed consent has been obtained, the following screening procedures will be performed and documented:

- Participant locator information
- Pre-test counselling
- Sexual risk behaviour questionnaire
- Pregnancy urine dipstick

- HIV rapid
- *HIV + confirmatory test (in the event of an HIV+ rapid test)
- Post-test counselling
- Targeted Physical examination
- Speculum examination and collection of
 - 1x Vulvo-vaginal swab for STI testing
 - 1x lateral vaginal wall swab to be applied to pH indicator and rolled on a glass slide for Nugent scoring
 - 1x lateral vaginal wall swab for qPCR and 16S rRNA (bacterial) & ITS (fungal) amplicon sequencing (Molecular transport medium [Qiagen])
 - 1x Lateral wall swab for culture (Amies-based transport solution, eg E-Swab [Copan]) (culture)
- STI/BV treatment as indicated by local symptomatic treatment protocol

If the in-/exclusion criteria are fulfilled, the participant will be enrolled in the study. All information will be recorded on a case report form (CRF or eCRF). In addition, contact information will be recorded on a locator form.

The screening and enrolment may not be done at the same visit.

Additional Screening Test (Amsel test for BV)

Participants who attend the screening visit, but who are not enrolled in the longitudinal study due to having bacterial vaginosis will still provide samples during their screening examination. Once approximately 100 such participants (screened but not enrolled) have been screened at each site, an additional pre-screening test (Amsel test for bacterial vaginosis) will be included to enrich for participants without BV. This will be done during the physical exam after the pregnancy and HIV tests and prior to the speculum examination. Participants who test positive for 3 or more of the Amsel criteria (thin homogenous/milky vaginal discharge, vaginal pH greater than 4.5, positive whiff test [fishy amine odour on addition of 10% KOH] and presence of clue cells on wet mount microscopy), will be screened out and not undergo the speculum exam.

Enrolment

The enrolment visit has to be conducted within 6 weeks of the screening visit. Before any study-specific screening procedures will be performed, all continuing consent will be obtained and documented. The investigator or delegate may discuss certain aspects of the study e.g. to determine continued eligibility. The following information will be collected and documented:

- Participant locator information re-confirmed
- Pre-test counselling
- Sexual risk behaviour questionnaire

- Pregnancy urine dipstick
- HIV rapid
- *HIV + confirmatory test (in the event of an HIV+ rapid test)
- Post-test counselling
- Speculum collection of
 - 1x Vulvo-vaginal swab for STI testing
 - 1x high vaginal wall swab for storage
 - 1x lateral vaginal wall swab to be applied to pH indicator and rolled on a glass slide for Nugent scoring
 - 1x lateral vaginal wall swab for qPCR and 16S rRNA (bacterial) & ITS (fungal) amplicon sequencing (Molecular transport medium [Qiagen])
 - 1x soft cup (cytokines) inserted for 30 mins
 - 1x Lateral wall swab for culture (Amies-based transport solution, eg E-Swab [Copan]) (culture)
 - 1 x lateral vaginal wall swab for storage (proteomic)
 - 1 x lateral vaginal wall swab for storage (metabolomic)
 - 1 x cytobrush for storage (transcriptomics)

Week 5

The mid-way week 5 visit has to be conducted when the participant is not menstruating, a ± 7 day visit window is allowable to account for this. Before any study-specific screening procedures will be performed, all continuing consent will be obtained and documented. The investigator or delegate may discuss certain aspects of the study e.g. to determine continued eligibility. The following information will be collected and documented:

- Participant locator information re-confirmed
- Pre-test counselling
- Sexual risk behaviour questionnaire
- Pregnancy urine dipstick
- HIV rapid
- *HIV + confirmatory test (in the event of an HIV+ rapid test)
- Post-test counselling
- Speculum collection of
 - 1x Vulvo-vaginal swab for STI testing
 - 1x high vaginal wall swab for storage
 - 1x lateral vaginal wall swab to be applied to pH indicator and rolled on a glass slide for Nugent scoring
 - 1x lateral vaginal wall swab for qPCR and 16S rRNA (bacterial) & ITS (fungal) amplicon sequencing (Molecular transport medium [Qiagen])
 - 1x soft cup (cytokines) inserted for 30 mins

- 1x Lateral wall swab for culture (Amies-based transport solution, eg E-Swab [Copan]) (culture)
- 1 x lateral vaginal wall swab for storage (proteomic)
- 1 x lateral vaginal wall swab for storage (metabolomic)
- 1 x cytobrush for storage (transcriptomics)

Exit

The exit visit has to be conducted when the participant is not menstruating, a ± 7 -day visit window is allowable to account for this. Before any study-specific screening procedures will be performed, all continuing consent will be obtained and documented. The investigator or delegate may discuss certain aspects of the study e.g. to determine continued eligibility. The following information will be collected and documented:

- Pre-test counselling
- Sexual risk behaviour questionnaire
- Pregnancy urine dipstick
- HIV rapid
- *HIV + confirmatory test (in the event of an HIV+ rapid test)
- Post-test counselling
- Physical examination
- Speculum collection of
 - 1x Vulvo-vaginal swab for STI testing
 - 1x high vaginal wall swab for storage
 - 1x lateral vaginal wall swab to be applied to pH indicator and rolled on a glass slide for Nugent scoring
 - 1x lateral vaginal wall swab for qPCR and 16S rRNA (bacterial) & ITS (fungal) amplicon sequencing (Molecular transport medium [Qiagen])
 - 1x soft cup (cytokines) inserted for 30 mins
 - 1x Lateral wall swab for culture (Amies-based transport solution, eg E-Swab [Copan]) (culture)
 - 1 x lateral vaginal wall swab for storage (proteomic)
 - 1 x lateral vaginal wall swab for storage (metabolomic)
 - 1 x cytobrush for storage (transcriptomics)

Self-collected samples

Self-collected low vaginal swabs in molecular transport medium [Qiagen] for qPCR and 16S rRNA (bacterial) & ITS (fungal) amplicon sequencing will be collected weekly and stored in a cool dry place and dropped at the CRS as soon as possible or at the next study visit.

Self-collected samples will also be taken at the week 5 study and week 10 exit visits. These will be compared to the nurse collected swabs at the same visits to evaluate differences between 16S rRNA and ITS fungal sequences possibly related to collection method (nurse collected vs self-collected)

Weekly questionnaire

Weekly yes/no questionnaires will be administered by telephone or WhatsApp along with reminders for self-collected samples. The questionnaires will collect sexual behaviour and exposure to antibiotics data to inform the study data.

The questionnaire will be administered at weeks 3-4 or 5 if the week 5 visit is delayed due to menstruation. As well as weeks 6-9 or 10 if exit is delayed due to menstruation.

Dissemination of study results

The dissemination strategy and activities will follow principles and best practices successfully tested by the partners in other projects and in line with the South African Guidelines for successful dissemination:

- All research results/reports will be duly reviewed, and a copy will be sent to relevant collaborators and partners involved in the project before these are disseminated and/or published.
- When appropriate, the reports will refer to other research projects and build on the existing results and literature.
- Research will be conducted following sound analysis and scientific practice principles, taking into account as much as possible policy requirements and needs.
- All public results will be accessible from the project website and usable for all parties who may benefit from them.

Dissemination timing

Dissemination activities are planned in accordance with the stages of the project. A number of dissemination activities will take place during the first 18 months of the project, the most significant dissemination activities will take place as final research results are available.

The dissemination activities are to be performed according to the following logical schedule:

